6.7.2 Instruction for prescribing and taking study treatment

There will be only one treatment phase in the extension study which is similar to the TtC phase of the core study and is defined as follows:

Figure 6-1 Treatment regimen

#The treatment interval can also be maintained if the investigator deems that the patient will not benefit from treatment interval extension

*week 54, depending on visit schedule

Treat-to-Control treatment phase (Baseline/Day 1 to Week 52):

Treatment intervals will be either 8 weeks, 12 weeks, 16 weeks, or 20 weeks. A subject must be discontinued from further study treatment if treatment is required every 4 weeks.

The participant will receive the first injection based on the next planned injection interval decided by the investigator at the last injection visit of the core study. For example, if a participant has the last injection visit at Week 60 of the core study, and the next planned injection interval is a q12w interval, the first injection visit for this participant will be planned at Week 8 of the extension study (12 weeks from Week 60 of the core study).

At each injection visit, DA should be assessed using anatomic and functional outcomes (e.g. SD-OCT, BCVA, etc.). Based on investigator's judgment of visual and/or anatomic outcomes, the treatment interval can be further extended by 4 weeks at a time, if there is no DA, i.e. no change in visual acuity and in other signs of the disease (e.g. IRF, SRF, hemorrhage, leakage, etc.).

Participants whose last injection interval in the core study is q16w and are without DA should be injected at another q16w interval in the extension study before extending to q20w in the extension study.

The treatment interval can also be maintained if the investigator deems the participant will not benefit from treatment interval extension.

If DA recurs, the interval should be shortened accordingly by 4 weeks at a time, to a minimal interval of 8 weeks.

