When the investigator decides to extend the treatment interval from 16 to 20 weeks, the investigator has the option to plan for an inspection visit 4 weeks before the next treatment visit (i.e. 16 weeks after the last treatment visit) to assess DA. If the study eye has no DA at the inspection visit, the participant will not receive study treatment at the inspection visit but 4 weeks later. If the investigator observes DA in the study eye at the inspection visit, the participant will receive study treatment at this visit. The treatment interval will then be reduced by 4 weeks and the next study treatment visit will be planned 12 weeks after the inspection visit.

When the investigator decides to extend the treatment interval from 8 to 12 weeks, the investigator has the option to plan for an inspection visit 2 weeks before the next treatment visit (i.e. 10 weeks after the last treatment visit) to assess DA. If the study eye has no DA at the inspection visit, the participant will not receive study treatment at the inspection visit but 2 weeks later. If the investigator observes DA in the study eye at the inspection visit, the participant will receive study treatment at the inspection visit. The next treatment interval will be reduced to 8 weeks. The same optional inspection visit 2 weeks earlier than the next treatment visit will be offered, when the investigator decides to extend the treatment interval from 12 to 16 weeks. If the study eye has no DA at the inspection visit, the participant will not receive study treatment at the inspection visit but 2 weeks later. If DA is observed in the study eye at the inspection visit, the participant will receive study treatment at the inspection visit. The next treatment interval will be reduced to 12 weeks. If the patient requires a reduction of the treatment interval down to 4 weeks, the patient will receive an injection at the visit, but will be discontinued from further study treatment at the next visit.

Regardless of treatment administration, Week 52 and Week 56 visits are mandatory. Participants who will receive study treatment at an inspection visit may also have a study visit

at Week 54; for these participants, the Week 54 visit will take place in lieu of the visit at Week 52 (unless this visit is inspection visit), respectively.

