² The number of weeks between visits will vary depending on the disease stability and length of intervals between injections as determined by disease activity assessment. Study treatment at the optional inspection visits (10 weeks after the last injection when the interval is extended from 8 weeks to 12 weeks, 14 weeks from the last injection when the interval is extended from 12 weeks to 16 weeks, and 16 weeks when the interval is extended from 16 to 20 weeks) is at the discretion of the investigator based on disease activity assessment.

³ Week 52 is the last visit when study treatment may be administered. End-of-Treatment visit will take place on Week 54 in lieu of Week 52 for the participants who have a planned injection visit on Week 54, unless the Week 52 visit is an inspection visit with injection administered.

⁴ Assessments at the Week 64 (EOS) visit of the core study will be used as the baseline.

⁵ May include visual acuity check, optic nerve perfusion, and tonometry, for safety assessment before and after IVT, as well as slit lamp examination, fundus examination before IVT. In case of an ocular AE, the assessments shall be recorded in the eCRF.

⁶ Additional ophthalmic examinations and images will be performed in case of any signs of intraocular inflammation, retinal vasculitis and/or retinal vascular occlusion.

⁷ OCT Angiography will only be performed at a subset of sites.

⁸ Study treatments are dependent on disease activity assessments and latest treatment interval.

⁹ A telephone follow-up on safety should be performed two weeks after the first injection (a window for the phone call is +14 days). From the second injection onwards, similar phone calls should be made at investigator's discretion per local practice.

¹⁰ ETD: Early treatment discontinuation applies to subjects who discontinue early from study treatment and continue in the study. This can occur at any time point. The assessments should be performed 4 weeks after the last injection of study drug. For visits conducted after ETD and up to Week 56 (end of study), while subject is on standard of care, only BCVA, new/any concomitant medications, and/or adverse events/ serious adverse events have to be recorded. Additional safety assessments and imaging can also be performed if required, as per investigators discretion. In addition, after ETD, subjects are not required to attend the mandatory visit at Week 52.

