2.1.1 General definitions

All the definitions, e.g. baseline, on-treatment period, are referring to the current extension study unless otherwise stated, e.g. baseline of the core study.

Study treatment is defined as brolocizumab 6 mg/0.05 mL.

Date of first administration of study treatment is defined as the first date when a non-zero dose of study treatment is administered and recorded on the case report form (CRF) dose administration page. The date of first administration of study treatment will also be referred to as start of study treatment.

Date of last administration of study treatment is defined as the last date when a non-zero dose of study treatment is administered and recorded on the CRF dose administration page. The last administration of study treatment will also be referred as end of treatment (EOT).

Study day will be calculated as:

- The date of the event (visit date, onset date of an event, assessment date etc.) – treatment start date + 1, if event is on or after the treatment start date;
- The date of the event (visit date, onset date of an event, assessment date etc.) – treatment start date, if event precedes the treatment start date.

Baseline/Day 1 is the end of study (EOS)/Week 64 of the core study.

On-treatment period is defined from Day 1 of the study to 30 days after the last administration of study treatment (i.e. EOT) or end of study (EOS), whichever is the latest.

Treatment interval is defined as the time period from one injection until the next injection. In this study, treatment intervals of q4w, q8w, q12w, q16w and q20w, meaning that there are 4, 8, 12, 16 and 20 weeks between 2 injections, are of special interest. The last (treatment) interval at Week X is referred to the last complete interval where injections at both ends of the interval have occurred on or before Week X. The last interval with/without disease activity is referred to the last interval with/without disease activity as observed at the end of the interval.

The first treatment is defined by the treatment interval of the core study. For example, a patient who started a 16-weeks interval at Week 56 of the core study will have the first treatment 8 weeks after the start of the extension study (i.e. 8 weeks after Week 64).

Participants will be assessed for eligibility based on inclusion and exclusion criteria for the extension study at the baseline visit.

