2.5.2 Statistical hypothesis, model, and method of analysis

The average change in BCVA from baseline of the extension study at Week 52 and Week 56 will be estimated by an analysis of variance (ANOVA) with baseline age categories, baseline BCVA categories and treatment arm in the core study included as fixed effects. The estimate of BCVA change will be accompanied by the 95% CI.

For the analysis of durability, the first step is to identify the last (treatment) interval with respect to Week 56 for each participant, i.e. the last interval for which injections have occurred at both ends of this interval before/at Week 56. If there is disease activity at the end of the last interval, then the last interval will be shortened by 4 weeks, down to a minimum of q4w. Subjects who do not receive any injection (or only one injection) of study drug in the extension study will be excluded from this analysis. In case of any treatment interruption or permanent study treatment discontinuation, the imputation techniques as per the estimand framework in [Section 2.5.3](#) will be considered. Then, the proportion of participants with last interval of q4w, q8w, q12w, q16w, and q20w will be specified. These proportions will be referred as the distribution of the last interval.

The distribution of the last interval with no disease activity up to Week 56 will be described based on counts and proportions of participants at 4-week, 8-week, 12-week, 16-week, and 20-week intervals. These proportions will be accompanied by 95% CIs. The counts and proportions will be accompanied by 2-sided 95% CIs inferred based on binomial distribution for each endpoint and 2-sided 95% simultaneous CIs inferred using the Goodman method (Goodman 1965). The Goodman method is used for obtaining simultaneous CIs for the parameters of a multinomial distribution, for example for a multinomial endpoint (4-week interval, 8-week interval, 12-week interval, 16-week interval, and 20-week interval).

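### Under the SAP scoring rule, the co-primary interval category of an eye already active at the inspection time can depend on whether the optional inspection visit was held, at all three extension steps

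*Protocol*

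**What the plan says.** Protocol 6.7.2 lets the investigator inspect before a lengthened interval ends. At the 16-to-20-week step, "the investigator has the option to plan for an inspection visit 4 weeks before the next treatment visit", that is, at week 16. If DA is seen there, the eye is injected at that visit and "The treatment interval will then be reduced by 4 weeks and the next study treatment visit will be planned 12 weeks" after it. If the eye is dry, "the participant will not receive study treatment at the inspection visit but 4 weeks later". At the two shorter steps the optional inspection falls 2 weeks before the planned injection (weeks 10 and 14); DA there leads to an injection and a next interval of 8 or 12 weeks respectively. Protocol Table 8-1, footnote 2, repeats that injecting at these visits "is at the discretion of the investigator based on disease activity assessment". Without an inspection, DA first comes to light at the planned injection visit, where the general rule applies: "If DA recurs, the interval should be shortened accordingly by 4 weeks at a time".

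SAP 2.1.1 sets the unit of analysis: "Treatment interval is defined as the time period from one injection until the next injection". The interval that counts is the last one with an injection at both ends. SAP 2.5.2 then says: "If there is disease activity at the end of the last interval, then the last interval will be shortened by 4 weeks", with q4w as the lowest category. The footnote to SAP Table 2-1 rounds an in-between duration down to the category below it.

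Neither Protocol 12.4.5 nor SAP 2.5.4 plans an analysis by inspection use.

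**The concern.** The category is meant to describe how long an eye goes without DA. Under these rules it also reflects whether someone looked early. Two eyes with the same disease course can fall in different categories because one investigator took the optional visit and the other did not. At the 16-to-20 step, the uninspected eye is counted as a 16-week interval without DA although week 16 of that interval was not examined.

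At stake is the reading of the q12w/q16w split, which is part of a co-primary endpoint, and of any statement about intervals of at least 16 weeks. At the two lower steps there is also a mismatch between documents. The SAP score for an inspected failure is one category below the next interval assigned by Protocol 6.7.2. At the 8-to-12 step an eye that the protocol sends to 8 weeks is scored q4w, the category for eyes that must stop study treatment under Protocol 9.1.1.

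**Working it through.** **Inputs.** Inspection times and next intervals: Protocol 6.7.2. Interval definition: SAP 2.1.1. Subtraction rule: SAP 2.5.2. Flooring: footnote to SAP Table 2-1. Planning shares of 29.2% (q12w), 12.7% (q16w) and 19.4% (q20w), and N = 250: Protocol 12.8. Visits are taken at nominal times, and DA present at an inspection is assumed to be still present at the planned visit if the eye is not inspected.

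**1. The plan's precision.** Width = 2 × 1.96 × √(p(1 − p)/n).
- q16w, n = 250: 2 × 1.96 × √(0.127 × 0.873/250) = 8.25% (stated 8.3%).
- q20w, n = 250: 2 × 1.96 × √(0.194 × 0.806/250) = 9.80% (stated 9.8%).

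Both reproduce. The q16w half-width is 8.25/2 ≈ 4.1 points.

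**2. Score by path, when the failed extension is the last complete interval.**

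| Step | Inspected, DA at inspection | Not inspected, DA at planned visit | Next interval assigned after DA at inspection |
|---|---|---|---|
| 16 to 20 | 16 − 4 = q12w | 20 − 4 = q16w | 12 weeks |
| 12 to 16 | 14 floored to 12; 12 − 4 = q8w | 16 − 4 = q12w | 12 weeks |
| 8 to 12 | 10 floored to 8; 8 − 4 = q4w | 12 − 4 = q8w | 8 weeks |

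Subtracting before flooring gives the same categories (14 − 4 = 10, q8w; 10 − 4 = 6, q4w). The score matches the assigned interval at the top step only. The bottom row depends on the SAP's q4w minimum. Protocol 4.1 states a minimum of 8 weeks for the same shortening; under that minimum both paths would give q8w.

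An eye dry at week 16 and active at week 20 is injected at week 20 whether or not it was inspected, so it scores 20 − 4 = q16w either way. Inspection changes the category only if DA is already present at the inspection time.

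**3. When the failed 16-to-20 extension decides the category.** Let w be the extension week that falls 16 weeks after the last injection, with Week 52 as the last injection.
- w ≤ 32: the next injection falls at w + 12 (inspected) or w + 4 + 16 = w + 20 ≤ 52 (uninspected). A later complete interval supersedes the failed one on both paths.
- w = 36 to 40: uninspected, the next injection would fall at 56 to 60, so the failed interval stands at q16w. Inspected, one further 12-week interval fits (ending at Week 48 to 52) and is scored instead; it cannot exceed q12w.
- w = 44 to 48: the failed interval is last on both paths, giving q12w against q16w directly.

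**4. Size at the 16-to-20 step.** Shift = f × a × u, where f is the share of participants whose last interval is a failed extension, a the fraction of these with DA already at week 16, and u the inspection uptake. None of the three is in the documents. The table takes the planning shares as the no-inspection case and moves u from 0 to 1.

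| f × a (assumed) | Participants of 250 | q12w | q16w | ≥16 weeks |
|---|---|---|---|---|
| 0 | 0 | 29.2% | 12.7% | 12.7 + 19.4 = 32.1% |
| 1% | 2.5 | 30.2% | 11.7% | 31.1% |
| 2% | 5 | 31.2% | 10.7% | 30.1% |
| 5% | 12.5 | 34.2% | 7.7% | 27.1% |

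On this reading the ceiling is 12.7 points, reached only if every q16w participant were an affected eye.

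**The case against.** The strongest defence is that investigator discretion to extend, maintain or inspect is part of the regimen, and that a single-arm descriptive study reports intervals under the regimen as used. In addition, "the treatment interval can be further extended by 4 weeks at a time, if there is no DA", and participants leaving the core study dry at 16 weeks should have another 16-week interval first. A first 20-week attempt is therefore normally preceded by a dry 16-week interval, and q16w then agrees with something observed. Both points stand, and they limit the likely size. They do not explain why the same disease course should score differently, and they do not resolve the mismatch at the lower steps.

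Several stronger readings are tempting but not supported:
- A reader might infer that every failed 16-to-20 extension scores q12w if inspected and q16w if not. Late DA (weeks 16 to 20) scores q16w either way, and early failures are superseded.
- A reader might infer that only this step is affected. That follows from the protocol's assigned intervals, not from the SAP score.
- A reader might assume that 20 to 40% of 250 end on a 20-week attempt and that 20 to 40% of those show DA, and infer that 10 to 40 participants (4 to 16 points) move. This counts every failure as already active at week 16, and its top exceeds the whole 12.7% q16w share.
- A reader might treat the share at 16 weeks or more as co-primary. It is protocol sensitivity estimand 1.3 to 1.5 and does not appear in SAP Table 2-1.
- A reader might infer biased core-arm comparisons. Protocol 6.4 keeps the core allocation confidential until database lock, so knowledge of the arm should not drive inspection use.

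**Conclusion.** The concern holds in a conditional form. For an eye with DA already present at the inspection time, in a failed extension that is the last complete interval, the SAP gives a category one step lower if the optional visit was held. This is so at all three steps, subject at the 8-to-12 step to the q4w minimum. At the two lower steps, Protocol 6.7.2 and SAP 2.5.2 with the Table 2-1 footnote also need reconciling for scoring.

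The size is unknown. An assumed 1 to 5% of participants affected at the 16-to-20 step moves 1 to 5 points between q12w and q16w; only the top of that range exceeds the half-width of about 4.1 points. This rests on nominal visit timing, on DA persisting to the planned visit, and on reading the planning shares as the no-inspection case. It limits what can be concluded about the q12w/q16w split but does not invalidate the endpoint.

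**What to change.** Change the SAP only; the treatment rules stay as they are.

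1. In SAP 2.5.2, state how an interval closed by an injection at a DA-positive inspection is scored, so that the score and the interval assigned by Protocol 6.7.2 are reconciled.
2. From IRT, where visits are registered (Protocol 6.6.1) and DA assessments recorded (Protocol 6.7.2), flag each participant's last interval as inspected or uninspected and DA yes or no, at all three steps. Flag separately the inspected failures that are followed by one further interval.
3. In SAP 2.5.4, add a table of the interval distribution under two recodings:
   - DA-positive inspection closings scored as if uninspected. This treats all failures at a step alike and is the upper bound.
   - Uninspected DA-positive closings scored as inspected failures. Label this a worst-case lower bound. Some of these eyes would have been dry at the inspection time, and an inspected eye with late DA keeps its higher score, so this recoding does not remove the dependence and should not be the sole basis for a claim.
4. Report any statement about 16 weeks or more with both bounds.

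The cost is SAP wording, the flags and one table, from data already collected. The downside is that the range for 16 weeks or more may look less favourable.

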4.1 Rationale for study design

The primary research interest is to assess the durability and functional outcome of brolocizumab treatment effect with treatment intervals up to 20 weeks, in all the eligible participants who will have completed the CRTH258A2303 (TALON) study, which compared the efficacy and safety of brolocizumab and aflibercept administered in the same TtC regimen with the treatment intervals from 8 to 16 weeks. Hence, this study is designed as an open-label, one-arm study. And the treatment interval adjustment will continue from the last treatment interval in the CRTH258A2303 (TALON) study, i.e. q8w, q12w and q16w, with an additional treatment interval of 20 weeks added in the extension study.

Co-primary efficacy endpoints based on treatment interval and BCVA were chosen to evaluate the benefits of treatment in terms of treatment durability and functional outcome, respectively:

Treatment intervals may be extended, reduced, or maintained, based on the evaluation of DA by investigators. The distribution of the last interval with no DA up to Week 56 will be analyzed. If there is DA during the last interval up to Week 56, the last interval will be shortened by 4 weeks down to a minimum of 8 weeks.

The co-primary efficacy endpoint based on BCVA (ETDRS letters) will also be assessed. Historically, the change from baseline in BCVA at a selected time point is considered appropriate as the primary efficacy endpoint in confirmatory nAMD studies, based on the

evidence available from existing anti-VEGF treatments in nAMD (e.g. ranibizumab, aflibercept).

The co-primary endpoint will be assessed as average change from the extension baseline in BCVA at Week 52 and Week 56. In the TtC phase, patients will receive injections at different intervals. Patients with longer treatment intervals may receive their last injection far earlier before the fixed assessment time point than those with shorter treatment intervals. A difference in the time since the last injection may affect BCVA gain and could introduce a bias on BCVA gain if measured at a single fixed assessment time point. Averaging change in BCVA from baseline at two time points 4 weeks apart will mitigate this potential bias.

Approximately 52 weeks of treatment in a TtC regimen, allows up to two consecutive q20w intervals and the evaluation of the long-term safety and efficacy of brolocizumab.

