The last potential study treatment may be administered at the Week 52 visit (or at the Week 54 visit for the participants who will have received study treatment at an odd number of inspection visits).

DA assessments will be recorded in the IRT system by the investigator or his/her delegate.

A DA assessment will also be performed at the Week 56/EOS visit; however, no study treatment will be administered.

The different types of study visits are summarized in [Table 6-3](#) with a description of when DA assessments and treatments take place.

Table 6-3 Disease Activity assessment and treatment occurrence according to visit type

Type	Study Period	DA Assessment	Treatment
Baseline visit	TtC-Phase	Yes	Only if treatment was planned according to the individual TtC regimen of the core study
Treatment visits	TtC-Phase	Yes	Yes
Inspection visits (optional)	TtC-Phase	Yes	Based on DA, as per investigator's judgement
Week 52/54*	TtC-Phase	Yes	Only if treatment was planned according to the individual TtC regimen
ETD visit and EOS visit (Week 56)	Follow-Up	Yes	No

Brolucizumab should be administered in the study eye on the day of the study visit, or, if this is not possible, within 3 days after the occurrence of the study visit (except for Baseline / Day 1, in which case study treatment administration should occur within the next 24 hours) or no later than within the visit window (± 14 days) as described in [Section 3](#) and [Section 8](#). When assessments and treatments take place on the same day, treatment must occur after completion of the efficacy assessments described in [Section 8.3](#) and pre-injection safety measures (tonometry, slit lamp and fundus examinations) described in [Section 8.4](#). If study visit assessments and the corresponding treatment occur on separate days, a repeat safety checkup should be performed prior to treatment of the eye and results should be documented in the source documents.

If any safety concern arises related to the study eye that, in the opinion of the investigator, may be further impacted by the study treatment or injection procedure, treatment needs to be cancelled.

IVT injection is contraindicated in participants with active intraocular or periocular infections and in participants with active intraocular inflammation; therefore, the investigators must verify that these conditions are not present in the study eye prior to every injection. Any adverse events must be recorded in the eCRF.

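### SAP 2.1.1 and 2.5.2 count disease activity only at the injection that closes the last interval, while Protocol 4.1 counts it anywhere in the interval, so activity seen at an uninjected inspection visit can go unscored.

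*Protocol*

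**What the plan says.** **How the interval is scored**

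- SAP 2.1.1: "Treatment interval is defined as the time period from one injection until the next injection". It adds: "The last interval with/without disease activity is referred to the last interval with/without disease activity as observed at the end of the interval".
- SAP 2.5.2: "If there is disease activity at the end of the last interval, then the last interval will be shortened by 4 weeks", with a floor of q4w.
- Protocol 4.1: "If there is DA during the last interval up to Week 56, the last interval will be shortened by 4 weeks", with a floor of 8 weeks.
- Protocol Table 12-1 and SAP Table 2-1 take off 4 weeks when there was DA. They do not say at what point in the interval the DA has to be seen.

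**What happens at an inspection visit**

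- Protocol 6.7.2, for the step from 16 to 20 weeks: "If the investigator observes DA in the study eye at the inspection visit, the participant will receive study treatment at this visit". After that, "the next study treatment visit will be planned 12 weeks after the inspection visit".
- Table 6-3, in the same section, describes treatment at inspection visits as "Based on DA, as per investigator's judgement".
- Table 8-1 footnote 2 says that study treatment at these visits "is at the discretion of the investigator based on disease activity assessment".
- Protocol 6.7.2 and Section 10 forbid an injection if there is any sign of intraocular inflammation (IOI). Section 6.7.2 also has treatment cancelled for a safety concern in the study eye.
- DA is assessed at inspection visits (Table 6-3), and DA assessments are entered in the IRT (6.7.2).

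**The concern.** An inspection visit without an injection does not end an interval as the SAP defines it. DA recorded there lies inside the interval, and the SAP text looks only at the closing injection. An interval with documented DA can therefore enter the co-primary analysis as DA-free, which is not what the endpoint's name promises. Protocol 4.1 would shorten the same interval. SAP Section 4, which lists changes from the protocol analyses, does not mention this difference.

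The effect runs in one direction. DA at the end of an interval is a special case of DA during it, so the SAP rule gives the same score as Protocol 4.1 or a longer one, never a shorter one. The q20w category matters most here, because Amendment 2 re-set the sample size around estimating it.

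**Working it through.** **1. The plan's own precision figure.** Inputs from Protocol 12.8: q20w share 19.4%, N = 250 and N = 503, 95% two-sided. Width = 2 × 1.96 × √(p(1−p)/N).

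- N = 250: 3.92 × √(0.194 × 0.806 / 250) = 9.80%. Stated: 9.8%.
- N = 503: 3.92 × √(0.194 × 0.806 / 503) = 6.91%. Stated: 6.9%.

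Both figures reproduce.

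**2. Can DA be recorded without an injection, within protocol?** Yes. IOI or a safety concern stops the injection whatever the DA finding, so this route does not depend on how the discretionary wording is read. If footnote 2 and Table 6-3 allow treatment to be withheld despite DA, there is a second route. SAP Table 2-1 keeps data collected after a treatment interruption, so these eyes stay in the FAS analysis.

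**3. Scores for an eye with DA at the 16-week inspection.** Each rule takes the injection-to-injection length, less 4 weeks if its DA condition is met.

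| Path | Length (weeks) | DA at closing injection | SAP 2.5.2 | Protocol 4.1 |
|---|---|---|---|---|
| A. Not injected at 16; injected at 20, no DA called | 20 | No | q20w | 20 − 4 = q16w |
| B. Not injected at 16; injected at 20 with DA | 20 | Yes | 20 − 4 = q16w | q16w |
| C. Injected at 16 | 16 | Yes | 16 − 4 = q12w | q12w |

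The rules disagree only on path A, by one category. Path A also arises at the other two steps:

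- 12 to 16 weeks, DA at the week-14 inspection, no injection, no DA called at week 16: q16w against 16 − 4 = q12w.
- 8 to 12 weeks, DA at the week-10 inspection, no injection, no DA called at week 12: q12w against 12 − 4 = q8w.

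The different floors (q4w in the SAP, 8 weeks in Protocol 4.1) do not affect any of these scores.

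**4. Size.** One eye is 1/250 = 0.4 percentage points (1/212 = 0.47 at the 212 completers used in the SAP's example). The assumed q20w group is 0.194 × 250 = 48.5 participants. The CI half-width is 9.8 / 2 = 4.9 points, or about 12 participants. Path A eyes would have to make up about 12.25 / 48.5 = 25% of the q20w group to move the estimate by one half-width.

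The documents give no frequency for path A. The shares below are assumptions:

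| Assumed share of q20w scores on path A | Participants | q20w if scored by Protocol 4.1 | q16w if scored by Protocol 4.1 |
|---|---|---|---|
| 2% | 1.0 | 19.0% | 13.1% |
| 5% | 2.4 | 18.4% | 13.7% |
| 10% | 4.9 | 17.5% | 14.6% |
| 20% | 9.7 | 15.5% | 16.6% |

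These eyes move from q20w to q16w, so the combined share at 16 weeks or more stays at 12.7% + 19.4% = 32.1%. Only path A at the 12-to-16-week step would lower it.

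**The case against.** Four counter-arguments deserve weight.

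- **The treatment passages can be read together.** Footnote 2 and Table 6-3 both tie treatment to DA, and DA is itself the investigator's judgement. The discretion may cover only whether DA is present, with treatment following. A reader might infer that treatment is flatly mandatory in one place and optional in another. The wording does not establish that much. It does leave room for a site to withhold treatment despite DA, and the IOI and safety route remains on either reading.
- **The SAP already has the wider rule.** SAP Table 2-1 shortens for DA without limiting it to the end of the interval, so it would be wrong to say that the SAP contains only the end-of-interval rule. But Table 2-1 then sits beside 2.1.1 and 2.5.2, which do set that limit and give the step-by-step derivation a programmer would follow.
- **The case needs a chain of events.** The inspection visit is optional and offered only when an interval is extended. DA must be recorded and not injected, must not be called at the closing injection, and the interval must be the last completed one. This stands, and it is why the effect is probably small.
- **The per-protocol set may remove such eyes.** Codes such as M_TRT04 and M_OTH02 might do so. They do not act on the FAS, which carries the primary estimand, and under the discretionary reading there may be no deviation to code.

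A reader might also infer that one week-16 finding can shift an eye by two categories, q12w against q20w. Those are paths C and A, which differ in when the eye was injected and in what was found at the closing injection. An injection-to-injection endpoint should separate them. The defect is the one-category disagreement on path A.

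**Conclusion.** The point holds as an inconsistency in the derivation of a co-primary endpoint. The detailed SAP rule can label an interval DA-free although DA was recorded within it, where Protocol 4.1 would shorten that interval by 4 weeks. The conclusion rests on the word during in Protocol 4.1 meaning any DA assessment in the interval, and on such a visit passing without an injection, which the protocol allows.

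The size is one category per affected eye, or 0.4 percentage points of the q20w share at N = 250, always towards longer durability. The 19.4% used for scale comes from simulations run before the urgent safety measures. A reader might infer that the durability result is materially inflated. The documents do not support that, because they give no frequency and about a quarter of q20w eyes would have to be affected to move the estimate by one CI half-width. The case for correcting it is that the rule should be unambiguous before the data are seen and the correction is cheap.

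**What to change.** **SAP, before database lock.** In 2.1.1 and 2.5.2, state that an interval is DA-free only if every DA assessment within it is negative, including inspection visits without an injection. Otherwise apply the existing 4-week shortening, as in Protocol 4.1. Use the same wording in SAP Table 2-1. List the participants with DA recorded at an uninjected inspection visit, with their score under the end-of-interval rule and under the aligned rule.

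**Protocol.** The text of Section 6.7.2, Table 6-3 and Table 8-1 footnote 2 must be reconciled on treatment at inspection visits. No view is taken here on which rule is right. The scoring change does not depend on the outcome.

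**Cost.** One derivation rule, matching table text and one listing in the SAP, and wording in the three protocol places. No new data are needed, since DA assessments are already recorded in the IRT.
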